6.5.4. Physicians Withdrawal Checklist (PWC)

The Physician Withdrawal Checklist (20 items; PWC-20) is a simple and accurate method used to assess potential withdrawal symptoms following cessation of treatment and will be measured at the end of study or follow-up visit. Each of the 20 items is rated on a 4-point Likert scale, with 0=not present, 1=mild, 2=moderate, 3=severe.

For each of the 20 items, a frequency distribution will be provided by treatment group for subjects with assessments at the time of discontinuation, and for subjects with assessments at the follow-up visit.

A total score (0 to 24) will be calculated by adding the scores of the following 8 items: Nausea-Vomiting, Diarrhea, Poor Coordination, Diaphoresis, Tremor-Tremulousness, Dizziness-Lightheadedness, Increased Acuity Sound Smell Touch, Paresthesias. If 1 or more items are missing, the total score will be left missing. Higher scores represent a more severe condition. The total score will be summarized with descriptive statistics by treatment group.

7. SUMMARY OF PLASMA CONCENTRATIONS FOR JNJ-42847922, M12, AND M16

Plasma concentrations for JNJ-42847922, and metabolites (M12, and M16) will be summarized by dose, day and time point, using descriptive statistics.

8. BIOMARKERS

Details of the biomarker analysis are provided in a separate document.

9. HEALTH ECONOMICS

9.1. Healthcare Resource Use Questionnaire (HRUQ)

Medical resource utilization data, associated with medical encounters, will be collected using the HRUQ during the double-blind and follow-up phases of the study.

The number and percentage of subjects who had at least one outpatient visit to a healthcare professional, related to their depression, in the period since the most recent assessment preceding each time point, will be summarized for each type of healthcare professional and for any healthcare professional by time point.

The number and percentage of subjects who had at least one emergency room visit without hospitalization, related to their depression, in the period since the most recent assessment preceding each time point, will be summarized by time point.

The number and percentage of subjects who had at least one day hospital or partial hospital visit (no overnight stay), related to their depression, in the period since the most recent assessment preceding each time point, will be summarized by time point.

The number and percentage of subjects who had at least one hospitalization (minimum one overnight stay), related to their depression, in the period since the most recent assessment preceding each time point, will be summarized by time point.

The total number of outpatient visits to each type of healthcare professional, related to depression, and the total number of outpatient visits to any healthcare professional, related to depression, in the period since the most recent assessment preceding each time point, will be summarized with descriptive statistics at each time point.

Likewise, the total number of emergency room visits without hospitalization, related to depression, the total number of day hospital or partial hospital visits (no overnight stay), related to depression, and the total number of hospitalizations (minimum one overnight stay), related to depression, will be summarized with descriptive statistics at each time point.

All summaries will be presented by treatment group.

REFERENCES

4. U.S. Department of Health and Human Services, Food and Drug Administration, Center for Drug Evaluation and Research (CDER), Center for Biologics Evaluation and Research (CBER). [2009] Guidance for industry drug induced liver injury: premarketing clinical evaluation. Available: <http://www.fda.gov/downloads/Drugs/.../Guidances/UCM174090.pdf>

ATTACHMENTS**ATTACHMENT 1 SCORING OF QLDS ITEMS**

I just want time to pass	True	1
	Not true	0
I feel hopeful about the future	True	0
	Not true	1
I find it hard to hold a conversation	True	1
	Not true	0
I like to know what is going on in the world	True	0
	Not true	1
I feel as if my life is wasting away	True	1
	Not true	0
I feel as if I am not in control of my life	True	1
	Not true	0
I am reluctant to leave the house	True	1
	Not true	0
On the whole, I enjoy the things I do	True	0
	Not true	1
I have lost all pleasure in life	True	1
	Not true	0
I feel as if I have nothing to offer anyone	True	1
	Not true	0
I turn away from people I care about	True	1
	Not true	0
I take good care of myself	True	0
	Not true	1
I am able to think about the future	True	0
	Not true	1
I just want to hide away	True	1
	Not true	0
I look forward to things	True	0
	Not true	1
I've forgotten what it's like to enjoy myself	True	1
	Not true	0

I can't be bothered with my friends	True	1
	Not true	0
I can cope easily with everyday tasks	True	0
	Not true	1
I cut myself off from other people	True	1
	Not true	0
It is difficult for me to make even simple decisions	True	1
	Not true	0
I feel as if I am a burden to people	True	1
	Not true	0
Most of the time I just sit and stare into space	True	1
	Not true	0
I can't face anyone	True	1
	Not true	0
I shut everything out	True	1
	Not true	0
I'm neglecting my appearance	True	1
	Not true	0
I can see the funny side of things	True	0
	Not true	1
I don't take in what people say to me	True	1
	Not true	0
I feel as if I'm letting everyone down	True	1
	Not true	0
I dread each coming day	True	1
	Not true	0
I enjoy my food	True	0
	Not true	1
I avoid people if I can	True	1
	Not true	0
I am reluctant to answer the door or the telephone	True	1
	Not true	0
My life has no meaning	True	1
	Not true	0
I am able to cope with everyday problems	True	0
	Not true	1

ATTACHMENT 2 CONVERSION OF RAW SCORE TO T-SCORE FOR PROMIS-SD

Sleep Disturbance 8a		
Short Form Conversion Table		
Raw Score	T-Score	SE*
8	28.9	4.8
9	33.1	3.7
10	35.9	3.3
11	38.0	3.0
12	39.8	2.9
13	41.4	2.8
14	42.9	2.7
15	44.2	2.7
16	45.5	2.6
17	46.7	2.6
18	47.9	2.6
19	49.0	2.6
20	50.1	2.5
21	51.2	2.5
22	52.2	2.5
23	53.3	2.5
24	54.3	2.5
25	55.3	2.5
26	56.3	2.5
27	57.3	2.5
28	58.3	2.5
29	59.4	2.5
30	60.4	2.5
31	61.5	2.5
32	62.6	2.5
33	63.7	2.6
34	64.8	2.6
35	66.1	2.7
36	67.5	2.8
37	69.0	3.0
38	70.8	3.2
39	73.0	3.5
40	76.5	4.4

*SE= Standard Error on T-score metric

Adult version

ATTACHMENT 3 CONVERSION OF RAW SCORE TO T-SCORE FOR PROMIS-SRI

Sleep-Related Impairment 8a Short Form Conversion Table		
Raw Score	T-Score	SE*
8	30.0	5.4
9	35.2	4.6
10	38.7	4.2
11	41.4	3.8
12	43.6	3.6
13	45.5	3.4
14	47.3	3.1
15	48.9	2.9
16	50.3	2.7
17	51.6	2.6
18	52.9	2.6
19	54.0	2.5
20	55.1	2.5
21	56.1	2.5
22	57.2	2.5
23	58.2	2.4
24	59.3	2.4
25	60.3	2.4
26	61.3	2.4
27	62.3	2.3
28	63.3	2.3
29	64.3	2.3
30	65.3	2.3
31	66.3	2.3
32	67.3	2.3
33	68.4	2.3
34	69.5	2.3
35	70.7	2.4
36	71.9	2.5
37	73.4	2.6
38	75.0	2.8
39	76.9	3.1
40	80.1	3.9

*SE= Standard Error on T-score

Adult version

ATTACHMENT 4 CRITERIA FOR TREATMENT-EMERGENT MARKEDLY ABNORMAL LABORATORY VALUES

Laboratory Parameter (unit)	Markedly Abnormal Limits	
	Low	High
Clinical Chemistry		
Albumin (g/dL) but SI unit = g/L	2.4→24	6.0 →60
Alkaline phosphatase (U/L)	N/A	250
Alanine transaminase (SGPT) (U/L)	N/A	200
Aspartate transaminase (SGOT) (U/L)	N/A	250
Bicarbonate (mEq/L) but SI unit=mmol/L	15.1→15.1	34.9→34.9
Bilirubin (direct) (mg/dL) but SI unit = μ mol/L	N/A	3.0 mg/dL→51.3 μ mol/L
Bilirubin (total) (mg/dL) but SI unit = μ mol/L	N/A	3.0 mg/dL→51.3 μ mol/L
Blood urea nitrogen (mg/dL) but SI unit=mmol/L	N/A	50 mg/dL→17.9 mmol/L
Calcium (mg/dL) but SI unit=mmol/L	6→1.497 mmol/L	12→2.994 mmol/L
Chloride (mEq/L or mmol/L)	94	112
Cholesterol (mg/dL) but SI unit=mmol/L	N/A	300→7.758 mmol/L
Creatine kinase (U/L)	N/A	990
Creatinine (mg/dL) SI unit= μ mol/L	N/A	3→ 265.2 μ mol/L
Gamma glutamyl transferase (U/L)	N/A	300 U/L
Glucose Plasma (mg/dL) but SI unit=mmol/L	40→ 2.204 mmol/L	300→16.653 mmol/L
High-density lipoprotein cholesterol (HDL) (mg/dL) but SI unit=mmol/L	35→0.905	N/A
Lactic acid dehydrogenase (LDH) (U/L)	N/A	500
Low-density lipoprotein cholesterol (LDL) (mg/dL) but SI unit=mmol/L	89→ 2.3015	160→4.1376 mmol/L
Phosphate (mg/dL) but SI unit=mmol/L	2.2→0.71038 mmol/L	8.1→ 2.61549 mmol/L
Potassium (mmol/L)	3.0	5.8
Sodium (mEq/L) but SI unit = mmol/L	125→125	155→155
Total protein (g/L)	50	N/A
Triglycerides (mg/dL) but SI unit=mmol/L	N/A	500→5.645 mmol/L
Uric acid (mg/dL) but SI unit= μ mol/L	1.5→89.22	10→594.8 μ mol/L
Hematology		
Hematocrit (%) - female	0.28	0.50
- male	0.24	0.55
Hemoglobin (g/dL) but SI unit=g/L	8→80	19→190
Hemoglobin A1c (%)	4	8
Neutrophils (%)	30	90
Monocytes (%)	N/A	20
Eosinophils (%)	N/A	10
Basophils (%)	N/A	6
Lymphocytes (%)	10	60
Reticulocytes (%)	0.5	1.5
Platelet count (10^9 /L; giga/L)	100	600
Red blood cell (RBC) count (10^{12} /L; tera/L) - female	3.0	5.5
- male	3.0	6.4
White blood cell (WBC) count (10^9 /L; giga/L)	2.5	15.0
Urinalysis		
Urine pH	N/A	6.5
Urine specific gravity	< 1.001	> 1.035

Note: Values should be flagged as markedly abnormally low if the value is less than the value indicated in the “Low” column. Likewise, values should be flagged as markedly abnormally high if the value is greater than the value indicated in the “High” column.

Note: The same limits apply to both males and females unless gender is indicated.

N/A = Not applicable.

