6.2. Clinical Laboratory Tests

Descriptive statistics will be presented for thyroid-stimulating hormone (TSH) and free thyroxine (FT₄), as well as all chemistry (including the lipid panel), hematology (including hemoglobin A1c [HbA1c]), and urinalysis (pH and specific gravity) laboratory parameters at each scheduled time point. In addition, change from baseline to all postbaseline time points will be summarized for chemistry, hematology, urinalysis (pH and specific gravity), TSH, and FT₄ parameters and displayed by treatment group.

The number and percentage of subjects with treatment-emergent postbaseline markedly abnormal postbaseline values will be presented by treatment group. Clinical laboratory test values will be considered “treatment-emergent markedly abnormal” (TEMA) using the criteria defined by the sponsor listed in Attachment 4. The identification of TEMA laboratory values is based on the postbaseline value being out of range while the baseline value is either missing or within the range given in Attachment 4. If postbaseline laboratory results are above the upper limit and the baseline value is below the lower limit, then the postbaseline abnormality will also be considered TEMA. The same applies to the postbaseline value being below the lower limit with the baseline value being above the upper limit.

In addition, the number of subjects with the following shifts in chemistry laboratory values from baseline to the maximum postbaseline time point will be presented:

- Glucose:
 - from <100 mg/dL to ≥ 126 mg/dL (normal to high)
 - from <100 mg/dL to [≥ 100 mg/dL - <126 mg/dL] (normal to borderline high)
 - from [≥ 100 mg/dL - <126 mg/dL] to ≥ 126 mg/dL (borderline high to high)
- Triglycerides:
 - from <150 mg/dL to ≥ 200 mg/dL (normal to high/very high)
 - from <150 mg/dL to ≥ 500 mg/dL (normal to very high)
 - from [≥ 150 mg/dL - <200 mg/dL] to ≥ 200 mg/dL (borderline high to high/very high)
 - from [≥ 150 mg/dL - <200 mg/dL] to ≥ 500 mg/dL (borderline high to very high)
 - from [≥ 200 mg/dL - <500 mg/dL] to ≥ 500 mg/dL (high to very high)
- Total Cholesterol
 - from <200 mg/dL to ≥ 200 mg/dL (normal to borderline high/high)
 - from <200 mg/dL to ≥ 240 mg/dL (normal to high)
 - from <200 mg/dL to [≥ 200 mg/dL - <240 mg/dL] (normal to borderline high)
 - from [≥ 200 mg/dL - <240 mg/dL] to ≥ 240 mg/dL (borderline high to high)
- HDL Cholesterol: from ≥ 40 mg/dL to <40 mg/dL (normal to low).

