The following conversion rules will be used: Glucose 1 mg/dL=0.05551 mmol/L; Triglycerides 1 mg/dL=0.01129 mmol/L; Total Cholesterol, HDL Cholesterol 1 mg/dL=0.02586 mmol/L.

The incidence of subjects with treatment-emergent ALT values >3 *upper normal limit (ULN), AST > 3 *ULN, or total bilirubin >2 *ULN will be presented for the double-blind phase. Additionally, incidence of treatment-emergent hepatic toxicity (suspected Hy's Law⁴ cases) defined as (ALT values >3 *ULN or AST values > 3 *ULN) AND total bilirubin values >2 *ULN will be presented for the double-blind phase. Similar to the markedly abnormal analysis, only subjects with baseline (ALT values ≤ 3 *ULN or AST ≤ 3 *ULN) (AND baseline total bilirubin values ≤ 2 *ULN for hepatic toxicity) (or if baseline value is missing) will be eligible for these analyses.

A listing of subjects with markedly abnormal laboratory values will be provided.

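### Three entries in SAP Attachment 4 (hematocrit unit, LDL low limit, glucose conversion) need correcting before the markedly-abnormal laboratory tables are programmed

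*SAP*

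**What the plan says.** Attachment 4 lists a low and a high limit for each analyte. Its first footnote reads: "Values should be flagged as markedly abnormally low if the value is less than the value indicated in the" Low column; the high side mirrors this. SAP Section 6.2 defines a TEMA value as a "postbaseline value being out of range while the baseline value is either missing or within the range given in Attachment 4". It adds that a move from beyond one limit to beyond the opposite one also counts.

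Three rows matter here:

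- **Hematocrit.** The row is headed "Hematocrit (%) - female", with limits 0.28 and 0.50; the male limits are 0.24 and 0.55.
- **LDL.** The row "Low-density lipoprotein cholesterol (LDL) (mg/dL) but SI unit=mmol/L" has a low limit of 89 mg/dL (2.3015 mmol/L) and a high limit printed as "160→4.1376 mmol/L".
- **Glucose.** The low limit is printed as "40→ 2.204 mmol/L", while Section 6.2 sets "Glucose 1 mg/dL=0.05551 mmol/L".

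For comparison, Attachment 4 gives total cholesterol and triglycerides no low limit and HDL no high limit. Section 6.2 treats total cholesterol below 200 mg/dL as normal (a move to 200 or more is labelled "normal to borderline high/high") and HDL of 40 mg/dL or more as normal.

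**The concern.** The limits will be programmed literally into the TEMA counts and into the listing of markedly abnormal values, so an entry with the wrong unit or an ill-placed limit goes straight into the safety tables.

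The hematocrit row could fail silently: limits on one scale and data on another would give a row with almost no flags, which looks like reassurance. The LDL row could do the opposite and fill with values that carry no safety meaning, in a comparison against quetiapine XR where metabolic effects are of interest. The glucose entry is a plain conversion slip. The sex-specific hematocrit low limits also look odd: the female low limit lies above the male one, while the high limits run the other way.

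**Working it through.** **Conversions.** Factors are from SAP Section 6.2 and limits from Attachment 4. Section 6.2 states 0.02586 for total and HDL cholesterol; the LDL row evidently uses the same factor.

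| Limit | Calculation | Printed (mmol/L) | Agrees |
|---|---|---|---|
| Glucose high | 300 × 0.05551 = 16.653 | 16.653 | yes |
| Triglycerides high | 500 × 0.01129 = 5.645 | 5.645 | yes |
| Cholesterol high | 300 × 0.02586 = 7.758 | 7.758 | yes |
| HDL low | 35 × 0.02586 = 0.9051 | 0.905 | yes |
| LDL low | 89 × 0.02586 = 2.3015 | 2.3015 | yes |
| LDL high | 160 × 0.02586 = 4.1376 | 4.1376 | yes |
| Glucose low | 40 × 0.05551 = 2.2204 | 2.204 | **no** |

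The glucose discrepancy is 2.204 − 2.2204 = −0.0164 mmol/L, and 2.204 / 0.05551 = 39.7 mg/dL. No whole mg/dL value and no value reported to 0.1 mmol/L changes its flag. At 0.01 mmol/L only 2.21 and 2.22 do. Calcium, phosphate and uric acid have no stated factor; their low and high limits imply a constant ratio, so they are at least internally consistent.

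**Hematocrit.** The other hematology percentages in Attachment 4 are on a 0–100 scale (for example HbA1c 4/8, neutrophils 30/90, lymphocytes 10/60). The TEMA rule with the male limits 0.24/0.55 gives:

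- Data as fractions: 0.42 falling to 0.20 is below 0.24 with baseline in range, so it is flagged. The limits work.
- Data in percent, 42 falling to 20: 20 is not below 0.24, so there is no low flag. It exceeds 0.55, but so did the baseline, so there is no high flag either.
- Data in percent, 42 rising to 60: not flagged, for the same reason.
- Data in percent, baseline missing, later value 42: flagged high, wrongly.

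With limits 24/55 and data in percent, 42 falling to 20 is flagged.

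**LDL.** Total cholesterol contains both HDL and LDL, so LDL cannot exceed total cholesterol minus HDL (measurement error aside). Take total cholesterol 148 and HDL 60, both on the normal side in Section 6.2. LDL is then at most 148 − 60 = 88 mg/dL, which is below 89 and flagged. A change from 95 to 88 mg/dL is a TEMA-low event.

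The documents give no LDL distribution, so the size rests on assumptions: normally distributed LDL, mean 100–130 mg/dL, SD 30–35 mg/dL, within-subject correlation 0.70–0.85, and no drug effect. Three post-baseline samples are used because the Time and Events Schedule has lipid panels at Weeks 6, 12 and 24. With 200,000 simulated subjects per scenario, the share with a TEMA-low LDL was:

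| Mean | Range over SD and correlation |
|---|---|
| 100 | 15.6%–23.0% |
| 115 | 12.0%–19.3% |
| 130 | 7.1%–13.2% |

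Per arm of 50 this is 0.071 × 50 = 3.6 to 0.23 × 50 = 11.5 subjects if all three samples are taken. Drop-out would lower it.

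**The case against.** The limits are the sponsor's own criteria, and the LDL low limit is correctly converted. The documents contain no LDL reference range, so a reader who infers that 89 is proved clinically wrong goes further than the text allows. That stands: what the documents show is an inconsistency with how the same SAP treats total cholesterol and HDL, and the fair request is to justify the limit or drop it.

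A reader might also infer that the low flags hide rises in LDL. They do not. Low and high flags are separate, the 160 mg/dL limit is untouched, and the opposite-side clause still catches a subject who moves from below 89 to above 160.

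Nor are the named metabolic endpoints at risk. The secondary lipid endpoints are triglyceride shifts and the glucose endpoints are fasting-glucose shifts. Both use cut-offs set in Section 6.2, not Attachment 4. LDL is not an endpoint, and it is also summarized descriptively with change from baseline.

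On hematocrit, 0.28/0.50 read naturally as fractions, and the documents do not state the delivered unit. If it is a fraction, only the label is wrong. Even in the bad case, hemoglobin and red-cell limits stand in the same table, and Protocol Section 11.8 promises a listing of results outside reference ranges. It would also be too strong to say the row could never flag anyone, since subjects without a baseline would be flagged. No passage contradicts the sex-specific low limits; they only look reversed.

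The glucose slip sits beside the correct value of 40 mg/dL and has almost no consequence.

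**Conclusion.** All three discrepancies are in the current SAP text, but they carry unequal weight.

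- **Hematocrit:** a definite mismatch of label and limits. The consequence is conditional: none if data are fractions; no fall detectable and false high flags for missing baselines if data are in percent.
- **LDL:** a low limit that flags subjects not abnormal on the SAP's own total cholesterol and HDL classes. About 7% to 23% of subjects would be flagged with no drug effect, a range that rests wholly on the assumed mean, SD and correlation. The harm is uninformative low flags.
- **Glucose:** a certain conversion error of 0.0164 mmol/L with negligible effect.

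A reader might conclude that the abnormal-laboratory table as a whole would mislead. The documents do not support that: it is not so for glucose, it depends on the data unit for hematocrit, and for LDL it is limited to the low side. These are descriptive safety tables; the primary endpoint is unaffected.

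**What to change.** Before the TEMA tables are programmed:

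1. Confirm the unit in which the central laboratory delivers hematocrit. Then either relabel the row as a fraction or restate the limits as 28/50 (female) and 24/55 (male). Check whether the two sex-specific low limits have been swapped.
2. Set the LDL low limit to N/A, or keep it with a stated justification against the central laboratory's range.
3. Replace 2.204 with 2.2204 mmol/L for the glucose low limit.

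The cost is a few corrected table cells in the SAP. Data collection, study conduct, the primary analysis and the shift endpoints do not change.

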## 1.2. Comparator Drug

### Quetiapine Fumarate Extended-release Tablets

Quetiapine extended-release (XR) will be included in this study as an active comparator to investigate potential differentiating features between JNJ-42847922 and quetiapine XR in the augmentation of selective serotonin reuptake inhibitor (SSRI)/serotonin-norepinephrine reuptake inhibitor (SNRI) treatment of MDD.

Quetiapine is a combined dopamine type 2 (D2) and serotonin type 2A (5HT2A) antagonist that belongs to the atypical antipsychotic class. Well-known class effects include neuroleptic malignant syndrome (NMS), somnolence/sedation, metabolic changes (eg, hyperglycemia, dyslipidemia, and weight gain), extrapyramidal symptoms (EPS) including tardive dyskinesia, orthostatic hypotension, and hematologic effects (eg, neutropenia and agranulocytosis), QT prolongation, seizures, and hyperprolactinemia. Additionally, cataract development has been observed in dogs after quetiapine exposure during chronic toxicity studies.

Although the immediate-release formulation was initially approved for use in schizophrenia, quetiapine XR has been shown to be effective for bipolar disorder and as adjunctive treatment with antidepressants for MDD. It is approved in the US and EU for the adjunctive treatment of MDD based on well-controlled studies.

For further information regarding quetiapine XR (including list of adverse reactions, dosage and administration, warnings and precautions, etc) refer to the local prescribing information.

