## **Clinical Laboratory Tests**

Blood samples for serum chemistry and hematology and a random urine sample for urinalysis will be collected. The investigator must review the laboratory results, document this review, and record any clinically relevant changes occurring during the study in the Adverse Event section of the CRF. The laboratory reports must be filed with the source documents. Clinical laboratory assessments (including TSH, FT4, hematology, serum chemistry, HbA1c, lipid panel, and urinalysis) should be performed under fasting conditions.

The following tests will be performed by the central laboratory:

- 
- Hematology Panel
    - hemoglobin
    - hematocrit
    - red blood cell (RBC) count
    - white blood cell (WBC) count with differential
    - platelet count
  
  - Serum Chemistry Panel
    - sodium
    - potassium
    - chloride
    - bicarbonate
    - blood urea nitrogen (BUN)
    - creatinine
    - glucose
    - insulin
    - aspartate aminotransferase (AST)
    - alanine aminotransferase (ALT)
    - gamma-glutamyltransferase (GGT)
    - total and direct bilirubin
    - alkaline phosphatase
    - creatine phosphokinase (CPK)
    - lactic acid dehydrogenase (LDH)
    - uric acid
    - calcium
    - phosphate
    - albumin
    - total protein
  
  - Lipid Panel
    - total cholesterol
    - triglycerides
    - low-density lipoprotein cholesterol
    - high-density lipoprotein cholesterol
  
  - Urinalysis
    - Dipstick
    - specific gravity
    - pH
    - glucose
    - protein
    - blood
    - ketones
    - bilirubin
    - urobilinogen
    - nitrite
    - leukocyte esterase
    - Sediment if dipstick result is abnormal
    - red blood cells
    - white blood cells
    - epithelial cells
    - crystals
    - casts
    - bacteria
  
  - Serum pregnancy testing, as determined by the investigator
  
  - TSH and FT4 (for subjects with known hypothyroidism who have been on stable treatment for at least 3 months prior to screening or for any subjects with an elevated TSH)
  
  - HbA1c
-

In addition, the following tests will be performed at the study site:

- Urine pregnancy testing, as needed per investigator's judgment
- Urine drug test (screening only): opiates (including methadone), cocaine, amphetamines, methamphetamines, cannabinoids, barbiturates, XTC and benzodiazepines. Urine drug screens will be done by the site using a dipstick
- Alcohol breath test

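### SAP Attachment 4 has no absolute neutrophil count, so counts as low as 0.75 x10^9/L, and lower for some subjects, can escape the treatment-emergent flag

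*SAP*

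**What the plan says.** Protocol 1.2 lists the well-known class effects of quetiapine, among them "hematologic effects (eg, neutropenia and agranulocytosis". Protocol 9.7 includes "white blood cell (WBC) count with differential" in the hematology panel, so both quantities needed for an absolute neutrophil count are available.

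SAP 6.2 counts subjects with TEMA laboratory values by treatment group, "using the criteria defined by the sponsor listed in Attachment 4". The hematology rows there that matter are:

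- "Neutrophils (%) 30 90" (low, high)
- "White blood cell (WBC) count (10^9 /L; giga/L) 2.5 15.0" (low, high)
- "Lymphocytes (%) 10 60" (low, high)
- "Monocytes (%) N/A 20" (no low limit; high)

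The note under the table makes the low flag a strict inequality: "Values should be flagged as markedly abnormally low if the value is less than the value indicated in the" Low column. A value exactly at the limit is not flagged.

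Under SAP 6.2, an out-of-range postbaseline value is treatment-emergent only if the baseline value is missing, within the limits, or beyond the opposite limit. Section 6.2 also plans descriptive statistics for hematology and a listing of markedly abnormal values. Neither Attachment 4 nor any SAP section derives an absolute neutrophil count.

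**The concern.** Two separate limits, one on the total and one on the percentage, do not bound their product well from the side that matters. A subject can sit just inside both limits and have a low absolute count. Another can cross the percentage limit while the absolute count is several times higher. The rule can thus order subjects wrongly on the quantity that defines neutropenia.

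Protocol 11.2 gives the study's main purpose as looking for features that separate the two drugs, and comparative safety is a secondary objective. For several other comparator class effects the SAP has tailored outputs: glucose and lipid shifts, HOMA, a composite definition of orthostatic hypotension, QTc categories, ESRS-A and a somnolence summary. It has none for low neutrophil counts. What is at stake is how far the neutrophil row can be relied on as a comparison between arms.

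**Working it through.** The documents state no absolute neutrophil count (ANC), so there is no plan figure to reproduce. The inputs are the Attachment 4 limits, the strict-inequality note and the baseline rule in SAP 6.2.

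**Formula.** ANC = WBC x neutrophils % / 100, in 10^9/L.

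**1. Lowest ANC with neither limit crossed.** If WBC is at least 2.5 and neutrophils are at least 30%, then ANC is at least 2.5 x 0.30 = 0.75. A grid over WBC (steps of 0.1) and neutrophils (steps of 1%) gives the same minimum.

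**2. Would another row catch it?** Not necessarily. Neutrophils 30%, lymphocytes 60% and monocytes 10% sum to 100%, and none crosses its limit. Some other differentials would raise a flag, for example lymphocytes above 60%, but in the lymphocyte row.

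**3. Subjects on each side of the rule, all with in-range baselines.**

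| WBC | Neutrophils % | ANC | Neutrophil or WBC low flag |
|---|---|---|---|
| 2.5 | 30 | 0.75 | none |
| 2.6 | 31 | 0.81 | none |
| 3.0 | 35 | 1.05 | none |
| 2.4 | 80 | 1.92 | WBC |
| 10 | 29 | 2.90 | neutrophil % |
| 12 | 28 | 3.36 | neutrophil % |

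The last subject is flagged with an ANC about four times that of the second, who is not (3.36 / 0.81 = 4.1).

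**4. Size of the gap for illustrative cut-offs.** These cut-offs are assumptions; the documents give none.

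- ANC below 1.0: unflagged combinations lie within WBC 2.5 to 3.3 and neutrophils 30 to 39%. At the edges, 3.3 x 0.30 = 0.99 and 2.5 x 0.39 = 0.975.
- ANC below 1.5: unflagged combinations lie within WBC 2.5 to 4.9 and neutrophils 30 to 59%. At the edges, 4.9 x 0.30 = 1.47 and 2.5 x 0.59 = 1.475.

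**5. Below 0.75.** Any such count must have WBC below 2.5 or neutrophils below 30%, so it crosses at least one limit. That does not make it TEMA. Take an illustrative subject with baseline WBC 12 and neutrophils 28% (ANC 3.36), and later WBC 2.6 and neutrophils 28% (2.6 x 0.28 = 0.73). In the neutrophil row the baseline is already below the low limit, so the later value is not treatment-emergent. In the WBC row, 2.6 is not below 2.5. The ANC has fallen from 3.36 to 0.73 with no TEMA in either row.

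**The case against.** The strongest reply is that a case missed by the TEMA flag need not be missed by the trial. Protocol 11.8 plans a listing of subjects with any result outside the laboratory reference ranges, separate from the markedly abnormal listing. Protocol 9.7 requires investigators to review laboratory results and record clinically relevant changes as adverse events, and SAP 6.1 tabulates treatment-emergent events by arm. This stands as mitigation. SAP 6.2 repeats only the markedly abnormal listing, but its silence does not cancel the protocol's out-of-range listing. Even so, a listing is not an incidence by arm, and adverse event tables depend on the investigator judging the change relevant. Summary statistics by group do not identify individual low counts.

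Second, neutropenia is not a named endpoint or an adverse event of special interest, and the row is labelled as a percentage within a general screen. That is true and limits the weight of the point. A reader might still take an empty neutrophil row to mean that no neutropenia occurred; the row does not claim this, and the limits could not support it.

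Third, any markedly abnormal cut-off leaves milder values unflagged by design, and the documents set no ANC threshold. This also stands: how much is missed depends on a limit still to be chosen.

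Two stronger readings are tempting and not supported. One is that low counts do go unflagged. They can, but only when WBC is at least 2.5 and neutrophils at least 30%, or when the baseline rule removes the flag; 0.75 needs both values exactly at their limits. The other is that the trial would fail to detect neutropenia or agranulocytosis. With in-range baselines every count below 0.75 is flagged in one row or the other, and the other safety routes remain.

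**Conclusion.** The point holds as a gap in one pre-specified safety screen. For subjects in range on both rows at baseline, an ANC as low as 0.75 x10^9/L can escape the TEMA flag. For subjects already below 30% neutrophils at baseline, an even lower count can escape it while WBC stays at or above 2.5. In the other direction, a high WBC with under 30% neutrophils is flagged despite a much higher absolute count. The SAP therefore gives no laboratory-based incidence of low absolute counts by arm, although the protocol names neutropenia as a comparator class effect.

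The 0.75 figure follows from the documents' own limits. The bands up to 1.0 or 1.5 rest on assumed cut-offs. No expected number of missed subjects can be derived from the documents. The primary endpoint is unaffected. This is a cheap improvement that should be made, not a flaw that undermines the trial.

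**What to change.** Add one hematology row to Attachment 4: absolute neutrophil count (10^9/L), calculated as WBC x neutrophils % / 100 or taken as the laboratory's reported absolute value. The sponsor should set its low limit and record it before unblinding; the documents give none and none is proposed here. For subjects in range on both existing rows at baseline, a limit at or below 0.75 would add no newly flagged subject.

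Apply the new row in the TEMA table by treatment group and in the markedly abnormal listing, with the existing baseline rule applied to the absolute count. Keep the current percentage limits, including the upper limit of 90. Subjects with a high WBC and a low percentage will still be flagged in the percentage row, but the new row will show that their absolute count is not low.

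The cost is one derived variable and one table row from data already collected. Because the existing limits stay, the number of flagged subjects may rise.
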